6.5.5 Routine 12-lead Electrocardiograms

Number and percent of subjects with 12 lead ECG abnormalities as well as number and percent of subjects whose 12 lead ECG reading changed from normal at baseline to abnormal will be tabulated by Analysis Visit.

The number and percentage of subjects who have treatment emergent changes toward worst category in the ECG interpretations assessed by investigators will be calculated. The interpretations are the followings: Normal, Abnormal-clinically relevant and Abnormal-not clinically relevant. Subjects who have both baseline and at least one post-baseline value will be included.

6.5.6 Pregnancies

A detailed listing of all pregnancies will be provided.

6.5.7 Other Safety-Related Assessments

None.

6.5.8 Subgroups of Interest for Safety

Safety data will be summarized for IA, IM and mixed IA/IM groups separately. Selected safety variables (treatment emergent adverse events and vital signs) will be summarized using summary statistics for the subgroups defined on the basis of the categorized variables listed below:

| Grouping variable | Subgroup |
|--------------------------|-----------------|
| Age group | < 12 years |
| | = 12 years |

6.6 Analysis of Pharmacokinetic

6.6.1 Estimation of Pharmacokinetic Parameters

Sampling times along with plasma concentrations of isavuconazonium sulfate levels will be displayed in listings. Descriptive statistics (e.g. n, mean, SD, minimum, median, maximum, coefficient of variation (CV), geometric mean and geometric CV will be provided for plasma concentrations of isavuconazole.

Plasma concentration data from this study will be used to support a population pharmacokinetic (PK) model developed for Isavuconazonium Sulfate. The results and the model development will be described in detail in a separate PPK report. All details of the pharmacokinetic analysis will be described in a separate analysis plan and a separate population pharmacokinetic modeling report will be written.

Existing population pharmacokinetic model will be updated based on isavuconazole plasma concentration data obtained from subjects who have at least 1 pharmacokinetic sample. Population pharmacokinetics and/or pharmacokinetic/pharmacodynamics analyses will be performed by modeling and simulation scientist.

6.7 Other Analyses

None.

6.8 Interim Analysis (and Early Discontinuation of the Clinical Study)

No interim analyses are planned for this study.

6.9 Analysis Windows

AEs and Vital signs will be summarized using Analysis Windows as below:

| Analysis Visits | Analysis Windows |
|------------------------|---|
| Baseline | Day(s) <=1 up to initiation of first dose |
| Day 2 | Day 2 |
| Day 3 | Day 3 |
| Day 7 | Day 5 to 9 |
| Day 14 | Day 12 to 16 |
| Day 21 | Days 19 to 23 |
| Day 28 | Days 26 to 30 |
| Day 35 | Days 33 to 37 |
| Day 42 | Days 40 to 44 |
| Day 49 | Days 47 to 51 |
| Day 56 | Days 54 to 58 |
| Day 63 | Day 61 to 65 |
| Day 70 | Days 68 to 72 |
| Day 77 | Days 75 to 79 |

Cont.

| | |
|----------------------|-----------------|
| Day 84 | Days 80 to 91 |
| Day 110 | Days 103 to 117 |
| Day 140 | Days 133 to 147 |
| Day 85 ¹ | Days 81 to 100 |
| Day 115 ¹ | Days 101 to 130 |
| Day 145 ¹ | Days 143 to 147 |
| Day 210 ¹ | Days 203 to 217 |
| Day 240 ¹ | Days 233 to 247 |

¹Applies to IM and IA/IM subjects.

See Appendix 1 for details of parameters for visit windows.

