2.2 Study Design

This is a phase 2, open-label, non-comparative, multicenter study to assess the safety, efficacy and pharmacokinetics of isavuconazonium sulfate in pediatric subjects for the treatment of IA or IM.

An approved informed consent form (ICF) must be obtained from the subject’s parent or legal guardian, and, if required, child assent prior to any study related procedures being performed.

Approximately 30 centers in the United States (US) and European Union (EU) are planned to enroll approximately 30 subjects ages 1 to < 18 years of age

The subjects will enter into screening anytime between days -5 to day 1 (predose). All subjects will be assigned to open-label treatment. Treatment will begin on day 1 and then subjects are followed for 60 days after the last dose for safety. Treatment will be administered until the subject has a successful outcome as judged by the investigator or for a maximum duration of 84 days (IA) or 180 days (IM), whichever occurs first.

After successful screening, all subjects will receive a loading regimen of isavuconazonium sulfate, which consists of a dose every 8 hours (\pm 2 hours) on days 1 and 2 (for a total of 6 doses), followed by once daily maintenance dosing for up to 84 days (IA) or day 180 (IM) of dosing. The first maintenance dose should start 12 to 24 hours after the administration of the last loading dose. Subsequent maintenance doses will be administered once daily (24 hours \pm 2 hours from the previous maintenance dose).

Blood sampling for the analysis of trough levels will be obtained from all subjects. The samples should ideally be drawn immediately prior to the next dose of study medication, but must be taken no earlier than 1 hour prior to the next dose on days 7, 14, 21, 42 and 84 or end of treatment (EOT). **In addition to the above, 24-hour pharmacokinetic samples will be obtained on any day between day 14 and day 42, while the subject is still receiving study drug, for subjects that consent to participation in the 24-hour pharmacokinetic assessment.** No additional samples are taken from IM subjects between day 84 through day 180.

Throughout the study, safety and tolerability will be assessed by the recording of AEs, vital signs, electrocardiograms (ECGs) and safety laboratory evaluations. All subjects will complete 2 follow-up visits (via telephone at the discretion of the investigator), 30 and 60 days, after the subject's day 84 (IA) /day 180 (IM) or EOT visit.

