3 SAMPLE SIZE

The sample size of approximately 30 subjects is planned. No formal sample size calculation was performed.

Evaluable subjects are subjects that have received at least 1 dose of study drug. Every effort will be made to achieve at least 5 evaluable subjects per age cohort: 1 to < 12 years of age and 12 to < 18 years of age. The sponsor reserves the right to stop enrollment if the cohort

requirements are not achieved. There will be no replacements for any subject that is enrolled but later determined to be non-eligible.

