6.5.1 Adverse Events

TEAE is defined as an AE observed after starting administration of the study drug through 30 days after EOT. The number and percentage of subjects with treatment-emergent AEs, serious adverse events (SAEs), AEs leading to withdrawal of treatment, and AEs related to study drug will be summarized by MedDRA system organ class, MedDRA High Level term, and MedDRA preferred term for overall subjects and by subjects in each age cohort. The number and percentage of AEs by severity will also be summarized. All AEs will be listed.

A study drug-related TEAE is defined as any TEAE with a causal relationship of YES by the investigator. The incidence of treatment emergent AEs will be summarized by relationship to study drug and severity for all subjects and by each age cohort. The protocol defines how Treatment Emergent AEs are determined. Although all AEs are collected, the summary Table will be based on the TEAEs.

Clinically significant out-of-range laboratory findings are to be determined and documented by the investigator/subinvestigator who is a qualified physician. Clinically significant changes will be recorded as AEs.

An overview table will include the following:

- Number of TEAEs,
- Number and percentage of subjects with TEAEs,
- Number of drug related TEAEs,
- Number and percentage of subjects with drug related TEAEs,
- Number of serious TEAEs,
- Number and percentage of subjects with serious TEAEs,
- Number of serious drug related TEAEs,
- Number and percentage of subjects with serious drug related TEAEs,
- Number of TEAEs leading to permanent discontinuation of study drug,
- Number and percentage of subjects with TEAEs leading to permanent discontinuation of study drug, and
- Number of deaths.

The number and percentage of subjects with TEAEs, as classified by SOC, High Level Term (HLT), and PT will be summarized. Summaries will be provided for the following:

- TEAEs

- drug related TEAEs,
- serious TEAEs,
- drug related serious TEAEs,
- TEAEs leading to permanent discontinuation of study drug,
- drug related TEAEs leading to permanent discontinuation of study drug,

The number and percentage of subjects with TEAEs, as classified by SOC and PT will be summarized by time interval. For each adverse event in a particular interval, a subject will be counted if there is an onset of a treatment-emergent adverse event regardless of onset in other intervals.

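### The by-interval TEAE table uses visit windows of unequal width, so a constant onset rate is expected to look like a rise over time (and, for IM subjects, a rise then a fall)

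*SAP*

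**What the plan says.** SAP 6.5.1 (Adverse Events) states: "The number and percentage of subjects with TEAEs, as classified by SOC and PT will be summarized by time interval". Its counting rule is that "a subject will be counted if there is an onset of a treatment-emergent adverse event regardless of onset in other intervals". The section does not say what the intervals are, which denominator applies, or whether any person-time is used.

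SAP 6.9 (Analysis Windows) states: "AEs and Vital signs will be summarized using Analysis Windows as below". The table that follows is built around visits. Day 2 and Day 3 are single days, the Day 7 to Day 77 windows each span the visit day plus or minus 2, and Day 84 covers Days 80 to 91. For IM and IA/IM subjects only, a Day 85 window covers Days 81 to 100, Day 115 covers "Days 101 to 130", and Day 145 covers "Days 143 to 147".

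The events in scope are set by SAP 6.5.1: "TEAE is defined as an AE observed after starting administration of the study drug through 30 days after EOT". Treatment continues until success or "for a maximum duration of 84 days (IA) or 180 days (IM), whichever occurs first" (SAP 2.2).

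SAP Appendix 1, to which 6.9 refers, gives different limits. Day 84 is D77 to D91 for IA and D82 to D86 for IM, Day 115 is D113 to D117, and there is no Day 85 visit.

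**The concern.** A visit window suits a measurement taken at a visit: one value is chosen, and the width only sets how far from the target day it may lie. An AE onset can fall on any day, so a wider window catches more onsets. If each interval reports the percentage of subjects with an onset, the percentage tracks the width of the interval as well as the risk.

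Safety is the first-listed objective, and there is no comparator arm in which the same artefact would appear. A reader who sees the percentage double at Day 84 could take it for late toxicity. In IM subjects, a drop at Day 145 could be taken for tolerance.

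**Working it through.** The plan states no event rate or expected percentage on this point, so there is no figure to reproduce. The check asks what the planned statistic would show if risk never changed.

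**Inputs.** Window limits come from SAP 6.9; width = last day − first day + 1. The onset rate λ per subject-day is an assumption, since neither document gives one; 0.002 to 0.1 is shown. The denominator is taken as subjects at risk, also an assumption.

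**Formula.** Expected share with at least one onset in a window of w days = 1 − exp(−λw).

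| Width (days) | SAP 6.9 windows | λ = 0.002 | λ = 0.01 | λ = 0.05 | λ = 0.1 |
|---|---|---|---|---|---|
| 1 | Day 2, Day 3 | 0.2% | 1.0% | 4.9% | 9.5% |
| 5 | Day 7 to Day 77; Day 145 (IM, IA/IM) | 1.0% | 4.9% | 22.1% | 39.3% |
| 12 | Day 84 | 2.4% | 11.3% | 45.1% | 69.9% |
| 20 | Day 85 (IM, IA/IM) | 3.9% | 18.1% | 63.2% | 86.5% |
| 30 | Day 115 (IM, IA/IM) | 5.8% | 25.9% | 77.7% | 95.0% |

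For example, at λ = 0.05 the Day 77 window gives 1 − exp(−0.25) = 22.1% and the Day 84 window gives 1 − exp(−0.60) = 45.1%.

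**IA subjects.** The step from Day 77 to Day 84 is 2.38-fold, 2.32-fold, 2.04-fold and 1.78-fold across the four rates. The step from Day 3 to Day 7 is 4.98-fold down to 4.13-fold. Up to Day 84 width produces a rise only. For a subject treated for the full 84 days, Days 85 to 91 of the Day 84 window fall after the last dose. They are still inside the 30-day TEAE tail, so the window also mixes on-drug and post-treatment time.

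**IM and IA/IM subjects.** From Day 115 (30 days) to Day 145 (5 days) the expected percentage falls 5.85-fold, 5.31-fold, 3.51-fold and 2.41-fold across the four rates. Days 81 to 91 (11 days) belong to both the Day 84 and the Day 85 window.

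**Under Appendix 1.** For IM subjects the Day 84 and Day 115 windows shrink to 5 days each, so the 20- and 30-day extremes and the Day 84/85 overlap disappear. For IA subjects the Day 84 window becomes D77 to D91, which is 15 days. The step from 5 to 15 days is 4.9% to 13.9% (2.86-fold) at λ = 0.01 and 22.1% to 52.8% (2.39-fold) at λ = 0.05. The IA rise therefore appears under either table.

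**Absolute size.** With 30 subjects at risk, the step from 5 to 12 days is 6.6 to 13.5 expected subjects at λ = 0.05, 1.5 to 3.4 at λ = 0.01, and 0.3 to 0.7 at λ = 0.002.

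**The case against.** Several limits are fair, and most of them stand.

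- **Linking the two sections is an inference.** SAP 6.5.1 does not cite 6.9. But 6.9 names AEs, SAP 6.9.1 uses imputed dates to allocate AEs to visits, and neither document gives other AE intervals. The inference is firm.
- **The widest windows are IM-only and disputed.** A reader might infer that percentages for all subjects rise and fall across a 1-to-30-day range. The documents do not support that. The 20-, 30- and final 5-day windows are footnoted to IM and IA/IM subjects, and Appendix 1 contradicts the 20- and 30-day ones.
- **Double counting is possible, not stated.** A reader might infer that an onset on Days 81 to 91 is counted twice. The SAP has no rule that enters an event in both windows, and none that assigns it to one of them.
- **IM numbers will be small.** Protocol 1.1 cites a paediatric cohort with 13% IM and an IM incidence about one tenth of that of IA. If enrolment followed those figures, 30 subjects would include about 3 to 4 with IM (30 × 0.13 = 3.9; 30/11 = 2.7). One child then moves a percentage by 25 to 33 points, which would swamp the width effect in that group.
- **The denominator is unstated.** With all treated subjects as denominator, attrition lowers the late windows. To cancel the Day 77 to Day 84 step, however, the number at risk would have to fall by about half between those adjacent windows (1 − 1/2.04 = 51% at λ = 0.05; 1 − 1/2.32 = 57% at λ = 0.01).
- **Rare terms hardly show it.** The table is by SOC and PT. At 0.002 per day the step is under one subject.

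**Conclusion.** The concern holds in limited form. As written, the by-interval table is expected to show a pattern produced by window width. For IA subjects that is a rise, about 2-fold from Day 77 to Day 84. For IM and IA/IM subjects it is a rise and then a fall, provided the 6.9 limits and not those of Appendix 1 are used. The size rests on an assumed constant onset rate and an at-risk denominator. It is most visible for SOC rows and common terms, shrinks in ratio at high rates, and is small in absolute terms for rare preferred terms.

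It would be wrong to conclude that the trial's safety assessment is compromised. The analysis is descriptive, the overall TEAE tables do not depend on these windows, and all AEs are listed. One descriptive table is affected, but the change is cheap and worth making.

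**What to change.** 1. In SAP 6.9, keep the visit windows for vital signs and remove AEs. Reconcile the 6.9 limits with Appendix 1.
2. In SAP 6.5.1, define contiguous, non-overlapping intervals from first dose to 30 days after last dose. The exposure bands in SAP 6.3 could serve if the open band above 84 days is closed at the end of the TEAE period and on-drug time is kept apart from post-treatment time.
3. For each interval report the number of subjects with an onset, the number at risk, and onsets per 100 subject-days at risk.

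The rate is the essential element. The 6.3 bands are themselves unequal (2, 5, 7, 7, 21, 14 and 28 days), so percentages over them would distort in the same way. A constant 0.05 per day appears as 5 onsets per 100 subject-days in every band, and 0.01 as 1. Contiguous intervals also pick up onsets on days that 6.9 leaves in no window (22 of Days 1 to 84).

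The cost is SAP wording and one reprogrammed table, using onset and dosing dates already collected. Rates in the small IM group will be imprecise; showing the counts and subjects at risk makes that plain.

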An Adjudication Committee will be utilized to confirm the diagnosis and overall, clinical, radiological and mycological response of IA or IM.

V. FLOW CHART AND SCHEDULE OF ASSESSMENTS

Figure 1 Flow Chart

EOT: end of treatment; IA: invasive aspergillosis; IM: invasive mucormycosis

Table 1 Schedule of Assessments (IA and IM Subjects) – Screening through Day 84 and IA Follow-up (30 and 60 Days Post-Day 84 or EOT [Last Dose of Study Drug])

Period	Screening	1	Treatment														IA Follow-up ²	
			2	3	7	14	21	28	35	42	49	56	63	70	77	84 or IA EOT ¹	110 (30 Day) IA or EOS	Day 140 (60 Day) IA or EOS
Day	-5 to 1 (predose)																	
Visit window (days)	none	none	none	none	± 2	± 2	± 2	± 2	± 2	± 2	± 2	± 2	± 2	± 2	± 2	± 7	± 7	± 7
ASSESSMENTS																		
Informed consent/assent	X																	
Verify eligibility criteria	X	X																
Demographics	X																	
Medical/surgical history	←																	→
EORTC/MSG diagnosis ³	←																	
Physical examination	X															X		
Height and weight ⁴	X															X		
Vital signs ⁵	X	X	X	X	X	X	X	X	X	X	X	X	X	X	X	X		
Routine 12-lead ECG ⁶	X	X			X	X		X				X				X		
Serum or BAL galactomannan	X																	
Efficacy response assessment ⁷	←																	→
Pharmacokinetic trough sampling ⁸					X	X	X			X						X		
Pharmacokinetic 24-hour sampling ⁹						X												
Clinical laboratory tests (chemistry, INR, hematology) ¹⁰	X				X			X				X				X		
Hepatic panel ¹¹	X			X	X	X	X	X	X	X	X	X	X	X	X	X		
Pregnancy test ¹²	X							X		X						X		
Prior and concomitant medications ¹³	←																	→
AE ¹⁴	←																	→
Isavuconazonium sulfate dosing ¹⁵		q8h	q8h	X	X	X	X	X	X	X	X	X	X	X	X	X		
Oral dosing acceptability assessment		X ¹⁶																
Mortality Status ¹⁷											X					X		

AE: adverse event; BAL: bronchoalveolar lavage; ECG: electrocardiogram; EORTC/MSG: European Organisation for Research and Treatment of Cancer/Mycoses Study Group; EOS: end of study; EOT: end of treatment; IA: invasive aspergillosis; IM: invasive mucormycosis; INR: international normalized ratio; q8h: once every 8 hours.

Footnotes continued on next page

1. If subject discontinues study drug prior to day 84 for IA subjects, all EOT procedures must be completed. If subject continues to allow consent, EOS information to be collected on follow-up.

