2. Follow-up is to be completed 30 (\pm 7) and 60 days (\pm 7) post-last dose from day 84 or EOT for IA subjects, and may be performed via telephone at the discretion of the investigator.
3. Diagnosis must be completed within 10 days of first dose.
4. Height is to be collected at baseline only. Weight is to be taken at baseline and day 84 or EOT.
5. Vital signs are to be measured within 1 hour prior to and approximately 1 hour after the end of each infusion. No additional vital signs are needed on dosing days for oral administration.
6. 12-lead ECG will be performed prior to study drug administration on each scheduled day.
7. Record assessments that are performed during the study to document response to antifungal therapy (e.g., serum galactomannan, radiology, mycological tests, changes in clinical signs and symptoms and any surgical procedure).
8. Pharmacokinetic trough samples should ideally be drawn immediately prior to the next dose of study drug, but must be taken no earlier than 1 hour prior to the next dose on days 7, 14, 21, 42 and 84 or EOT.
9. For both intravenous and oral dosing: 24-hour pharmacokinetic samples will be obtained on any one day between day 14 and day 42, while the subject is still receiving study drug, for subjects who consent to participation in the 24-hour pharmacokinetic assessment. The intravenous pharmacokinetic samples will be collected as follows: within 1 hour prior to the start of the intravenous isavuconazonium sulfate infusion. This sample will be the same as the trough sample prior to dose, if it coincides with scheduled days 14, 21 or 42, and immediately after the completion of the intravenous infusion (no more than 5 minutes after); and within 4 to 10 hours after the start of the intravenous infusion and within 16 to 24 hours after the start of the intravenous infusion (must be obtained before the start of the next infusion).
The oral pharmacokinetic samples will be collected as follows: within 1 hour of the next oral dose (this sample will be the same as the trough sample prior to dose, if it coincides with scheduled days 14, 21 or 42); 1 hour post dose (\pm 10 minutes); 3 hours post dose (\pm 10 minutes); 4 hours post dose (\pm 10 minutes); within 6 to 8 hours (\pm 30 minutes) of study drug administration; and 24 hours (within 1 hour before next study drug administration) after study drug administration.
10. Clinical (safety) laboratory samples will be assessed by the local laboratory.

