1. within 1 hour prior to the start of the intravenous isavuconazonium sulfate infusion (this sample will be the same as the trough sample prior to dose, if it coincides with scheduled days 14, 21 or 42);
2. immediately after the completion of the intravenous infusion (no more than 5 minutes after);
3. within 4 to 10 hours after the start of the intravenous infusion; and
4. within 16 to 24 hours after the start of the intravenous infusion (must be obtained before the start of the next infusion).

Subjects receiving oral administration:

The 24-hour pharmacokinetic samples will be obtained for oral dosing as follows:

1. within 1 hour of next oral dose (this sample will be the same as the trough sample prior to dose, if it coincides with scheduled days 14, 21 or 42);
2. 1 hour post dose (\pm 10 minutes);
3. 3 hours post dose (\pm 10 minutes);
4. 4 hours post dose (\pm 10 minutes);
5. within 6 to 8 hours (\pm 30 minutes) of study drug administration; and
6. 24 hours post dose (within 1 hour before next study drug administration) after study drug administration.

No additional samples will be taken from IM subjects after day 84.

Throughout the study, safety and tolerability will be assessed by the recording of AEs, vital signs, ECGs and safety laboratory evaluations. This includes assessments at 14 days, 28 days and 56 days. All subjects will complete 2 follow-up visits. At the discretion of the investigator, follow-up visits may be conducted via telephone with the subject, the subject's parent or the subject's legal guardian, 30 and 60 days after the subject's day 84 (IA)/day 180 (IM) or EOT visit.

If subject discontinues study drug prior to day 84 or day 180, all EOT procedures must be completed. If subject continues to allow consent, end of study (EOS) information will be collected 30 and 60 days after EOT.

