9 APPENDICES

9.1 Appendix 1 Visit Windows

The value used is that which is closest to the defined assessment day and also within visit day windows. If two values are equally close, the latter is used in the analysis.

All the assessments will be allocated to electronic Case Report Form (eCRF) visit based on the table below.

Visit Windows

| Protocol visit | Target day | Visit window | Visit number |
|------------------------|------------|--------------------------------------|--------------------|
| Screening and Baseline | ≤D1 | D-5 to D1 | Pre dose period |
| V1 (Day1) | D1 | D1 | Visit 1 |
| V2 | D2 | D2 | Visit 2 |
| V3 | D3 | D3 | Visit 3 |
| V4 | D7 | D5 to D9 | Visit 4 |
| V5 | D14 | D12 to D16 | Visit 5 |
| V6 | D21 | D19 to D23 | Visit 6 |
| V7 | D28 | D26 to D30 | Visit 7 |
| V8 | D35 | D33 to D37 | Visit 8 |
| V9 | D42 | D40 to D44 | Visit 9 |
| V10 | D49 | D47 to D51 | Visit 10 |
| V11 | D56 | D54 to D58 | Visit 11 |
| V12 | D63 | D61 to D65 | Visit 12 |
| V13 | D70 | D68 to D72 | Visit 13 |
| V14 | D77 | D75 to D79 | Visit 14 |
| V15 | D84 | IA D77 to D91 or IM D82 to D86 | Visit 15 IA EOT |
| IA EOS | D110 | D103 to D117 | IA Follow-up |
| IA EOS | D140 | D133 to D147 | IA Follow-up |
| V16 | D115 | D113 to D117 | IM Visit 16 |
| V17 | D145 | D143 to D1146 | IM Visit 17 |
| V18 | D180 | D173 to D187 | IM Visit 18 EOT |

| | | | |
|--------|----------------------------|--------------|--------------|
| IM EOS | D210 (or 30 day EOS) | D203 to D217 | IM Follow-up |
| IM EOS | D240 (or 60 day EOS) | D233 to D247 | IM Follow-up |

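### The IA follow-up visits are labelled and windowed around Days 110 and 140 instead of Days 114 and 144, and no window counts from last dose, so early stoppers' follow-up visits are misfiled

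*SAP*

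**What the plan says.** Protocol Section 2.2.1 places the two follow-up visits "30 and 60 days after the subject's day 84 (IA)/day 180 (IM) or EOT visit". Footnote 2 to Table 1 allows ±7 days on each and counts them "post-last dose from day 84 or EOT for IA subjects". The column heads of the same table read "110 (30 Day) IA or EOS" and "Day 140 (60 Day) IA or EOS", each with a ±7-day visit window.

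SAP 6.9 carries the labels over, with "Days 103 to 117" for the first visit and "Days 133 to 147" for the second. Appendix 1 repeats both ranges. Section 6.9 opens with "AEs and Vital signs will be summarized using Analysis Windows as below". Appendix 1 is wider: "All the assessments will be allocated to electronic Case Report Form (eCRF) visit based on the table below".

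Treatment can end before Day 84 once the investigator judges the outcome successful (protocol 2.2.1). A subject who stops early is still followed 30 and 60 days after end of treatment (EOT). No window in either SAP table is counted from last dose. In Appendix 1 the follow-up rows for invasive mucormycosis (IM) at least mention a 30-day or 60-day alternative to the study day. The IA rows do not.

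**The concern.** Two things do not fit. The printed study days do not follow from the stated rule, and the ±7 days around them describe different calendar days from the footnote under the same table. In addition, a fixed study-day window can locate a visit timed from last dose only when the last dose falls near the assumed day.

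What is at stake is the filing of follow-up information. A visit held within the protocol's limits may get no analysis visit, may sit under a treatment-visit label although the subject is off drug, or may be shown as the other follow-up visit. In a study of about 30 subjects, a few such cases can alter a by-visit table.

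**Working it through.** **Inputs.** Timing rule and ±7 days: protocol 2.2.1 and Table 1 footnote 2. Labels: Tables 1 and 2. Windows: SAP 6.9, using the rows that apply to IA subjects. Maximum IA treatment: 84 days.

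**Step 1: reproduce the plan's figures.** The SAP windows are the Table 1 labels ± 7: 110 ± 7 = 103 to 117 and 140 ± 7 = 133 to 147. The labels do not follow from Day 84: 84 + 30 = 114 and 84 + 60 = 144. Working back, 110 − 30 = 80 and 140 − 60 = 80, so they imply a last dose on Day 80. The IM labels are right: 180 + 30 = 210 and 180 + 60 = 240.

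**Step 2: subject with last dose on Day 84.**

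| Visit | Allowed days (footnote 2) | SAP window | Allowed days with no window |
|---|---|---|---|
| 30-day | 114 ± 7 = 107–121 | 103–117 | 118–121: 4 of 15 (27%) |
| 60-day | 144 ± 7 = 137–151 | 133–147 | 148–151: 4 of 15 (27%) |

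The exact targets, Days 114 and 144, lie inside the windows. Only a visit 4 to 7 days late loses its place.

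**Step 3: early stoppers, visits exactly on target.** Let L be the last-dose day. The 30-day visit is filed correctly if 103 ≤ L + 30 ≤ 117, so L = 73 to 87. The 60-day visit needs 133 ≤ L + 60 ≤ 147, which gives the same range. With the 84-day maximum, both are right for L = 73 to 84. For L of 72 or less, neither visit lands in its own window.

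Where the visits go for L = 1 to 83, counted in last-dose days:

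| Filed under | 30-day visit | 60-day visit |
|---|---|---|
| Treatment-visit window | 47 | 27 |
| No window | 25 | 30 |
| Day 110 window | 11 (correct) | 15 (wrong visit; L = 43–57) |
| Day 140 window | 0 | 11 (correct) |
| Total | 83 | 83 |

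Examples:
- L = 28: Day 58, filed as Day 56; Day 88, filed as Day 84.
- L = 42: Day 72, filed as Day 70; Day 102, no window.
- L = 56: Day 86, filed as Day 84; Day 116, filed as the 30-day visit.
- L = 70: Days 100 and 130, neither in any window.

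Appendix 1 starts its IA Day 84 window at Day 77 rather than Day 80. Days 77 to 79 already belong to the Day 77 visit, so the split between treatment window, no window and follow-up window is unchanged.

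**Step 4: adverse events.** SAP 6.5.1 counts an event in an interval by its onset, and TEAEs end 30 days after EOT. For a Day 84 finisher that is Day 114, so the uncovered Days 118–121 and 148–151 lie beyond the TEAE period. Within that period, however, Days 92–102 have no IA window: 11 of the 30 days from Day 85 to Day 114. A follow-up window starting at last dose + 23 (Day 107) would not by itself cover onsets 1 to 22 days after last dose.

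**The case against.** The best reply is that little of substance depends on these windows. Much of it stands:

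- AEs are placed by onset date, not by the date of the contact at which they are reported. A late telephone call therefore does not displace an event.
- Vital signs are not scheduled at the IA follow-up visits, and SAP 6.5.4 summarises them only to Day 84 or EOT.
- All AEs are listed. Overall TEAE counts run from first dose to 30 days after EOT regardless of visit windows.
- Footnote 2 already gives sites the right rule.

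A reader might infer that safety data are lost, or that off-drug events are counted as on-treatment. The documents do not support that. The SAP specifies no table that separates on-treatment from post-treatment AEs, and an onset on Day 72 shown under Day 70 carries the correct study day.

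A reader might also take the ±7 days on the Day 84 visit to allow a last dose on Day 91, which would put most of the allowed 30-day range beyond Day 117. The protocol defines EOT as the date of last dose, with a maximum of 84 days for IA, so that case is not provided for and forms no part of this point.

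The reply does not remove the wrong labels, the conflict between column and footnote, or the Appendix 1 rule, which covers all assessments and has no provision for IA subjects who stop early.

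**Conclusion.** The point holds as an error of labelling and allocation. Days 110 and 140 are each 4 days too early. For a Day 84 finisher, 4 of 15 allowed days at each visit have no window. For IA subjects who stop before Day 73, neither on-target follow-up visit reaches its own window.

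The consequence is limited to assigning follow-up assessments to visits and to by-visit or by-interval summaries. Overall TEAE counts, listings, and mortality through Days 42 and 84 are unaffected.

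Three assumptions matter. Follow-up is counted from last dose, as in footnote 2. Visits in Step 3 fall exactly on target. The counts in Step 3 give each last-dose day equal weight, so they describe coverage and do not predict numbers of subjects; the documents give no distribution of treatment duration.

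**What to change.** - **Protocol Table 1:** relabel the IA follow-up columns Day 114 and Day 144, or name them as 30 and 60 days after last dose, so that the columns agree with footnote 2.
- **SAP 6.9 and Appendix 1:** define the follow-up visits for all subjects as last dose + 23 to + 37 days and last dose + 53 to + 67 days. State that these take precedence over study-day windows for any assessment after EOT.
- **AE interval tables:** assign onsets after last dose to one contiguous post-treatment interval, so that events starting 1 to 22 days after last dose are also covered.

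The cost is a correction to three tables and a small amount of programming by days since last dose. Data collection and visit timing do not change.
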